Improving Holding Function of the Hemiplegic Hand with Chemodenervation

NCT02459951

Date: 4-29-2016

Improving Holding Function of the Hemiplegic Hand with Chemodenervation

Specific Aims

Inserting and holding an object in the hand is what we mean by 'hand as a holder' function. After a stroke, the hand typically lacks voluntary finger extension that opens the hand. Simultaneously, the hand is also subjected to involuntary contraction of finger flexor muscles that close the hand, resulting in clenched fist and thumb-in-palm deformities. Despite these typical hemiplegic configurations, persons with stroke may be able to insert an object into the hand by wiggling and pushing it into the hemiplegic hand with their uninvolved hand, though struggle is often present and failure is frequent. A main goal of this project is to demonstrate that 'hand as a holder' function can be improved by blocking overactive muscles with medication. The main measure of hand function improvement will be 'transit time' i.e. the time it takes for the uninvolved hand to insert an object into the hemiplegic clenched fist and hold it independently.

This pilot study of 9 patients aims to demonstrate reliability and validity of a digital video method that will be used to measure 'transit time'. It also aims to establish initial statistical support for improved object transit time into the hemiplegic clenched fist after Botox A injections. [Botox A, injected directly into offending muscles, is a neuromuscular blocking agent that was approved by the FDA in 2010 to treat spasticity, a form of involuntary muscle contraction, in finger and wrist flexor muscles of persons sustaining a hemiplegic stroke.]

Experimental Design

Study hypothesis: Given hemiplegic patients, of stroke etiology, with a neurally driven clenched fist, who may also have a thumb-in-palm and/or a flexed wrist and who have severely impaired voluntary finger and thumb extension, we hypothesize that 'hand as a holder' function will improve after chemodenervation of relevant finger, thumb and wrist muscles selected by clinical examination.

The study objective is a pilot demonstration of the clinical hunch that objects will be inserted for holding by the hemiplegic hand more quickly and easily after chemodenervation, and, in some cases, insertion of larger diameter objects will be achieved as well.

Inclusion Criteria

1. Participant (or legal guardian) has been informed of the study procedures, participant is willing to comply with the study protocol and written informed consent has been given.
2. Age greater than 35 and less than 80 years.
3. Participant has experienced a documented, anemic or hemorrhagic, unilateral (right or left) hemiplegic stroke 1 year or more prior to enrollment.
4. While aphasia and hemianopsia are not absolute criteria for exclusion, a participant must be able to understand verbal and visual instructions and demonstration regarding task protocol.
5. A 'resting' wrist angle 0 is an inclusion criterion. It will be measured as follows: The forearm of a participant will be placed on a foam wedge, allowing the wrist and hand to hang down over the front wall of the wedge. Wrist angle will be measured with a clinical goniometer.
6. Spasticity is present in finger flexors and thumb coupled with marked voluntary paresis of finger extension (no finger has more than half range of active extension at any joint). By squeezing the examiner's finger, participants will have demonstrated, at least, some detectable voluntary contraction of finger flexors. Participants may have a flexed wrist (typical).
7. Impaired sensation is acceptable but participants must be aware that they are holding something, as tested clinically.
8. Participants present with at least two finger flexors with an Ashworth score ≥ 3
9. Participant will have moderate motor severity as defined by an upper limb Fugl-Meyer (14) motor scores between 21-50.
10. Participant does not have joint capsule contractures as determined by clinical exam.

11. Participant may have tightness/shortening of extrinsic finger flexors but composite extension of wrist and fingers comes to at least neutral (i.e. fingers and wrist can be brought to neutral position simultaneously).

Exclusion Criteria

1. Profound sensory loss/absent touch sensation.
2. Known hypersensitivity/allergy to Botox A.
3. Acute illness or unresolved medical/psychiatric conditions at time of assessment.
4. Participant is pregnant or breast-feeding.
5. Participant had Botox injections 4 months previously.
6. Clenched fist associated with tenodesis of an extended wrist i.e. resting position of wrist is > 0

Project Design

9 participants with spastic hemiparesis greater than 12 month's duration will be studied using a repeated measures design. Two baseline sessions separated by at least 3 days will be conducted along with one post Botox treatment session, approximately 3 to 5 weeks later. [The peak response of Botox for spasticity has been reported as 4 weeks (1). Our clinical experience also confirms that four weeks is a reasonable time to expect a treatment effect. However, practical considerations such as participant schedules and transportation encourage us to target 4 weeks 7 days.] Each participant will use their uninvolved hand to insert cylinders with 5 graduated diameters into the receiving hemiplegic hand. The same scripted instructions will be used for all participants, including visual demonstration of cylinder insertion through the web space entrance of the hand. Cylinder diameters will range between 0.5 and 2.5 inches and will be approximately similar in weight and height. Each session will consist of 15 trials (5 cylinder diameter sizes times 3 insertions for each diameter → 15 trials, the order of diameter size being randomized). A 30 second trial duration will be allotted. Three synchronized Sony AS100VR recording cameras will provide side, front and top views, strategically placed to observe the "onset" time i.e. time of

initial object contact with the hemiplegic hand and the “offset” time i.e. the time the uninvolved hand lets go of the cylinder and the hemiplegic hand holds the cylinder independently. [The hemiplegic hand must visibly be holding the object independently for 5 seconds without being dropped or otherwise supported by contact with other parts of the body or the environment.] Using Final Cut Pro video software, playback of the synchronous views of the three cameras will be used by two independent coders to measure onset and offset times in order to calculate object transit time. Given that all insertions will be video recorded, it may be useful for coders to score qualitative aspects of performance when a participant doesn't meet the 5-sec criterion of unsupported grasp. In addition, we are unaware of another measure of holding function that could be administered to test convergent validity, emphasizing one aspect of the novelty of this project's work.

One reason why this pilot is exploratory and small in number is to learn more about variability in the primary measure. In addition, we will note stability of task performance as well the presence of short-term practice effects that may materialize across baseline sessions. In order to be informative, treatment effect would have to be greater than short-term practice effects. Since persons with hemiparesis would not have prior experience with insertion of the specific objects used in this project, we plan to give participants two practice trials prior to the experimental ones in each of the three sessions.

TREATMENT PLAN: Injection of Botox A will be done using customized dosing because participants typically present variable configurations reflecting the variability of underlying muscle involvement. Clinical assessment and judgment will be used to determine which muscles contribute to the hand deformities of a given participant. Therefore, we expect that any of the following muscles may be injected using the following typical ranges: 20-60 U into the flexor digitorum sublimis (up to 3 sites), 20-60 U into the flexor digitorum profundus (up to 3 sites), 10-40 U into the interossei (up to 4 sites), 20-40 U into flexor pollicis longus, 10-20 U into adductor pollicis, 10 U into flexor pollicis brevis, 40-70 U into flexor carpi radialis, 30-60 U into palmaris longus and 20-40 U into flexor carpi ulnaris. Maximum dose (if all

muscle were injected maximally) totals 400 U. Current clinical practice uses an upper limit of 600 U in adults.

Data Analysis Plan

Statistical Methods

Utilizing Final Cut Pro software, two coders independently used three synchronized camera views to identify onset and offset times of cylinder insertion in order to calculate cylinder Transit Time (Offset Time minus Onset Time). During a practice period, coding rules were established and coder training practice was done with hemiparetic volunteers. A concordance correlation coefficient (CCC) [Lin LI. A concordance correlation coefficient to evaluate reproducibility. *Biometrics* 1989; 45:255-68] was computed as a measure of agreement between the two coders. Results indicated that the CCC for Onset Time was 0.961 (95% CI: 0.938, 0.996); the CCC for Offset Time was 0.998 (95% CI: 0.993, 0.999) and the CCC for Transit Times was 0.977 (95% CI: 0.945, 0.991).

Statistical Methods

Protocol 1: Analysis of Transit Time [time to insert a cylinder into the affected hand]

The log-transformed Transit Times were analyzed using a linear mixed effects (LME) model with the fixed effects of cylinder diameter (0.5, 1, 1.5, 2, 2.5 inches), evaluation session (Pre 1, Pre 2 and Post Treatment) and their interaction. The random effects of subject and evaluation session were included to allow for correlation among repeated measures for the same participant. Though two statistical models were considered, the model reported here included Pre2 and Post-treatment Transit Times as repeated measures of response variable, and Pre1 Transit Times as a covariate in the model, using the average of the three cylinder insertion trials for each cylinder diameter and evaluation session. The residuals of the LME model were evaluated for consistency with the assumption of the normal distribution.

The data included 69 (17%) of trials with missing transit times meaning that a subject was not able to do the insertion. A linear mixed effects methodology is appropriate for modeling data with missing observations if the ‘misses’ (i.e. participant was unable to insert a cylinder into the affected hand within 30 seconds) are ignorable or missing at random. For non-ignorable ‘misses’, it is required to specify the response mechanism (a probability model for missing indicator or non-response). A repeated measures logistic regression model was used to model the missing data indicator and investigate whether the ‘misses’ depended on cylinder diameter, evaluation session or Transit Times observed at the first baseline session (Pre1).

The data analysis was performed in SAS (SAS Institute Inc., Cary, NC, USA) and R (R Core Team (2016). R: A language and environment for statistical computing. R Foundation for Statistical Computing, Vienna, Austria. URL <http://www.R-project.org/>.)

Protocol 2: The counts of successful holds (i.e. participants had to hold a given cylinder independently with the affected hand for 5 seconds) in 3 trials for each cylinder diameter were modeled using a repeated measures negative binomial model with the 3 trials as an exposure.

The predictors of expected number of successful holds included the cylinder diameter and evaluation session (Pre-1 baseline session, Pre-2 baseline session, and Post-treatment). The interaction between cylinder diameter and evaluation session was also considered, but was not a significant predictor of mean successful holds. The model allowed for correlation among counts for multiple cylinder diameters and evaluation sessions for the same participant using an exchangeable correlation structure. Correlation among counts was estimated using the GEE approach (as implemented in SAS PROC GENMOD, SAS Institute Inc., Cary, NC, USA).

Primary Outcome Measure(s):

1. Geometric Ratios of Log-transformed Transit Time [Time Frame: transit times were measured at Pre-injection session 2 and Post-injection session]

Secondary Outcome Measure(s):

2. Incidence Rate of Successful Holds [Time Frame: evaluation sessions Pre1, Pre2, and Post]

3. Incidence Ratio of Successful Holds [Time Frame: evaluation sessions pre1, pre2, and post]

4. Modified Ashworth Scores (MAS) for injected muscles [Time Frame: evaluation sessions Pre1, Pre2, and Post]; [MAS are obtained to verify that a biological effect of neurotoxin is, indeed, present] .

Subject Recruitment Plan: The MCAL treats over 400 patients a year and clenched fist problems occur in 20%. We anticipate no difficulty in obtaining 9 participants for this pilot study.

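### The documents do not say that the video coders were masked to session, and inter-coder agreement cannot show a bias that both coders share

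*Combined protocol and SAP*

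**What the plan says.** The design is before-and-after in one group: "9 participants with spastic hemiparesis greater than 12 month's duration will be studied using a repeated measures design". The order of sessions is fixed: "Two baseline sessions separated by at least 3 days will be conducted along with one post Botox treatment session". Within a session the trials are "5 cylinder diameter sizes times 3 insertions for each diameter", and the order of diameters is the only thing randomised.

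Transit time is offset minus onset, read from video. Project Design plans that "playback of the synchronous views of the three cameras will be used by two independent coders to measure onset and offset times", and the Data Analysis Plan reports that "two coders independently used three synchronized camera views to identify onset and offset times of cylinder insertion". Onset is the first contact of the object with the hemiplegic hand. Offset is "the time the uninvolved hand lets go of the cylinder and the hemiplegic hand holds the cylinder independently", with the added condition: "The hemiplegic hand must visibly be holding the object independently for 5 seconds".

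The safeguards described are these event definitions, the three camera views, coding rules and training ("During a practice period, coding rules were established and coder training practice was done with hemiparetic volunteers"), and a concordance correlation coefficient (CCC) between coders of 0.977 for transit time (95% CI 0.945 to 0.991).

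The primary outcome compares transit time at Pre2 and Post. Experimental Design states the expected direction: faster insertion after injection.

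**The concern.** The safeguards make the two coders agree with each other. None of them conceals which session a clip comes from. Both uses of independence, in Project Design and in the Data Analysis Plan, describe coders working separately from one another. That is a different property from not knowing whether the hand has been injected.

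Some of the coding is judgement. First contact is fairly sharp. The offset is less so, because release must coincide with independent holding, and a participant who works an object into a clenched fist may let go by degrees or more than once. Whether the hold is unsupported for 5 seconds is also decided by eye, and that decision feeds the successful-hold outcomes too.

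At stake is the primary answer, together with the aim of showing that the video method is valid. With no concurrent control, a session-linked shift in coding has nothing to cancel against. It could also make the treatment effect appear to exceed the practice effect, which Project Design sets as the condition for an informative result.

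**Working it through.** **1. Number of clips.** Inputs from Project Design: 9 participants, 3 sessions, 15 trials per session. 9 × 3 × 15 = 405 trials. The Data Analysis Plan reports 69 missed trials as 17%; 69/405 = 0.170, so 405 is the denominator in use.

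**2. Search for masking.** The whole document was read for any statement on masking, blinding, concealment of session, de-identified clips or shuffled clip order. There is none. There is also no statement that coders knew the session, and none on who the coders were.

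**3. How a shared shift enters the primary ratio.** On the log scale the contrast is log(Post) − log(Pre2). If both coders shorten Post times by a fraction d, the contrast moves by log(1 − d) and the ratio is multiplied by (1 − d). Averaging three trials or two coders does not reduce this. In the reported model, Pre1 is a covariate with the same value for the Pre2 and the Post record of a given participant and diameter, so it cannot absorb a shift present only at Post.

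**4. Why the CCC does not detect it.** Write the two readings as X = T + b + e1 and Y = T + b + e2, where b is a shift both coders apply at Post. In X − Y the shift b cancels, so disagreement is unchanged. A simulation illustrates this with assumed values: 405 trials treated as independent, log-normal times with median 5 s and log-SD 0.8, no true effect, coder error set to give a CCC of 0.977, 2,000 repetitions.

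| Shared shortening at Post | Mean CCC | Post/Pre2 ratio (true value 1) |
|---|---|---|
| 0% | 0.977 | 1.00 |
| 5% | 0.976 | 0.95 |
| 10% | 0.976 | 0.90 |
| 20% | 0.974 | 0.80 |

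The ratio moves by a fifth while the CCC moves by 0.003, well inside its stated interval.

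**5. Illustration in seconds.** The documents give neither a mean transit time T nor any basis for a shift s, so both are assumed. With no true effect, false ratio = (T − s)/T.

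| Shift s | T = 3 s | T = 5 s | T = 10 s |
|---|---|---|---|
| 0.25 s | 2.75/3 = 0.92 | 4.75/5 = 0.95 | 9.75/10 = 0.975 |
| 0.5 s | 2.5/3 = 0.83 | 4.5/5 = 0.90 | 9.5/10 = 0.95 |

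This uses a single mean time, not the mixed model over five diameters, and it leaves out the other route, in which a lenient hold judgement turns a miss into a timed trial.

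**The case against.** The strongest objection is that the text is silent. A reader might infer that the coders were unmasked and that the reported effect is therefore biased. The documents support neither step: they do not say that the coders knew the session, and they do not say that they did not. This stands, and the point is worded accordingly.

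Second, contact and release are physical events read on playback from three synchronised views by trained coders with set rules. That leaves much less room for bias than a rating scale. If the CCC applies to clips like those in the study, agreement of 0.998 for offset suggests that the events are rarely ambiguous, so large shifts are less plausible. This also stands, and it is why the 0.25 s row is the more cautious illustration and why a 1 s shift would be an extreme case. It does not exclude small shared shifts. Nor is it clear whether the CCC was computed on practice volunteers or on study sessions.

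Third, this is an exploratory pilot of nine, and masked coding would leave practice, time and participant-expectation effects in the same contrast. True, but those effects are hard to remove in this design, whereas coder masking is within easy reach because every insertion is recorded.

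Fourth, the Data Analysis Plan reports coding and modelling in the past tense, so new prospective text may come too late for this dataset. That stands, and the fix therefore includes recoding.

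**Conclusion.** The concern holds in a limited form. As written, the plan does not keep the coders from knowing the session, and in a single-arm, fixed-order study with a declared expected direction a shift shared by both coders would appear as a treatment effect. Training, coding rules, the CCC and the Pre1 covariate do not address it.

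No actual bias is shown, and its size cannot be obtained from the documents. The false ratios of 0.92 to 0.975 (0.25 s) and 0.83 to 0.95 (0.5 s) rest on assumed shifts and assumed mean times of 3 to 10 s. They show what such an error would do, not how likely it is. The change is worth making because it protects the primary ratio at low cost.

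**What to change.** In Project Design, after the sentence on the coders, add text to this effect: *Recordings from Pre1, Pre2 and Post are cut to single trials, stripped of date and session labels, given random codes and shuffled across sessions. The two coders are told neither session nor treatment status. Coding of a participant's clips starts only after that participant's Post session.*

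In the Data Analysis Plan, state whether the coders knew the session and whether the CCC came from practice volunteers or study clips.

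If coding was done with session known and the video is kept, have the existing two coders recode a relabelled, shuffled sample of the 405 trials and report the resulting Post/Pre2 ratio beside the main result as a sensitivity analysis.

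Costs: done prospectively, the work is file cutting, relabelling and shuffling with the coders already in place and no extra visits, but coding waits for the Post session. Recoding takes modest coder time, and coders may recall clips they have already seen. In both cases a visibly relaxed hand may partly unmask them. Masking the coders does nothing about practice, time or participant-expectation effects, so the report should still name those.

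### The pilot is small partly to learn the variability of transit time, but the reported model cannot separate trial-to-trial or untreated session-to-session variance; a supplementary model on data already coded can

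*Combined protocol and SAP*

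**What the plan says.** The Project Design section describes the structure: "9 participants with spastic hemiparesis greater than 12 month's duration will be studied using a repeated measures design". On sessions it says "Two baseline sessions separated by at least 3 days will be conducted along with one post Botox treatment session". Each session has "15 trials (5 cylinder diameter sizes times 3 insertions for each diameter". So there are three replicate insertions at every diameter, and two sessions before any treatment.

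The same section gives the purpose: "One reason why this pilot is exploratory and small in number is to learn more about variability in the primary measure". It continues: "we will note stability of task performance as well the presence of short-term practice effects that may materialize across baseline sessions". It also sets a condition for an informative result, that the "treatment effect would have to be greater than short-term practice effects".

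Statistical Methods, Protocol 1, first describes a mixed model of log transit time with session at three levels (Pre1, Pre2, Post) and random effects of subject and session. It then says that two models were considered. The one reported has Pre2 and Post as responses, has "Pre1 Transit Times as a covariate in the model", and is fitted "using the average of the three cylinder insertion trials for each cylinder diameter and evaluation session". The section counts 69 trials (17%) as misses, meaning insertions not completed within 30 seconds.

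The primary outcome is the ratio of transit times between Pre2 and Post. No SD, variance component or test-retest coefficient for transit time appears among the outcomes. The one reliability statistic is the concordance coefficient between the two coders.

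**The concern.** Replicate trials are what identify trial-to-trial variance. A pair of untreated sessions is what identifies ordinary session-to-session variance. The design collects both, and the reported model then averages away the first and moves half of the second to the right-hand side of the equation. The coder concordance does not fill the gap, because it measures agreement on the same video rather than stability of the patient's performance. The model for successful holds keeps all three sessions but concerns a different outcome.

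At stake is one stated reason for running a pilot of this size. Without the two components, the study cannot say whether more insertions per session would sharpen the measure, or how far transit time moves between two untreated days. The point concerns variance only. The mean change from Pre1 to Pre2 is a separate matter.

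**Working it through.** **1. Confirm the structure.** From Project Design: 9 participants × 3 sessions × 5 diameters × 3 insertions = 405 trials. The stated misses give 69/405 = 17.0%, which matches the 17% in Protocol 1. Of the 405 trials, 9 × 2 × 5 × 3 = 270 are untreated.

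**2. Trial-to-trial variance.** Each participant-by-diameter-by-session cell with three trials carries 3 − 1 = 2 degrees of freedom.
- Pre1 and Pre2: 9 × 5 × 2 × 2 = 180 df with no misses.
- All three sessions: 9 × 5 × 3 × 2 = 270 df with no misses. A first or second miss in a cell costs 1 df each and a third costs none. So 69 misses cost between 46 (23 cells wholly missed) and 69, leaving 224 to 201 df.
- How the misses split between sessions is not stated. If all 69 fell at baseline and none shared a cell as a third miss, 180 − 69 = 111 df would remain.
- Averaged data: 0 df.

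The 95% interval for an SD runs from √(df/χ²₀.₉₇₅) to √(df/χ²₀.₀₂₅) times the estimate:

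| df | lower | upper |
|---|---|---|
| 270 | 0.922 | 1.092 |
| 180 | 0.907 | 1.115 |
| 111 | 0.884 | 1.151 |
| 8 | 0.675 | 1.916 |

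The trial-to-trial SD is therefore well estimated even with 9 participants.

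**3. What averaging does to the residual.** If logs are averaged and all three trials are completed, residual variance = (trial variance)/3 + cell-level variance. Take assumed log-scale SDs of 0.5 (trial) and 0.2 (cell): √(0.2² + 0.5²/3) = 0.351. A trial SD near 0 with a cell SD of 0.35 gives about the same residual. Doubling to six trials would bring the first to √(0.2² + 0.5²/6) = 0.286 and leave the second at 0.35. The averaged data cannot tell these cases apart.

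**4. What moving Pre1 does to the session variance.** Let the untreated session variance be s² and the variance of individual treatment response be t². At session level the Pre2-to-Post change has variance 2s² + t². A model with one common session variance attributes half of this to each session, giving s² + t²/2. With only one untreated session among the responses, s² and t² are not separable. A Pre1/Pre2 analysis has 9 participant contrasts, hence 8 df for s².

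**5. Simulation check** (3,000 subjects, no misses, logs averaged, all variances assumed). Setting A had trial variance 0.36 and untreated session variance 0.09. Setting B had 0.09 and 0.01, plus varying treatment response and a cell-level term.

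| Estimate | A | B |
|---|---|---|
| Reported model: session variance | 0.094 | 0.090 |
| Reported model: residual variance | 0.121 | 0.122 |
| Individual trials, Pre1/Pre2: trial variance | 0.361 | 0.090 |
| Individual trials, Pre1/Pre2: session variance | 0.090 | 0.011 |

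A 4-fold difference in trial variance and a 9-fold difference in untreated session variance leave the reported model's output almost unchanged. The individual baseline trials recover both. The sizes depend on the assumed variances; the confounding in steps 3 and 4 does not.

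**The case against.** The strongest objection is that the plan promises little. It says it will learn more about variability and note stability. It names no component, and a descriptive summary might meet that wording. No follow-on trial is described. This stands as a limit on weight: the three-part decomposition is the natural reading of a design with replicates and two baselines, but the text does not demand it.

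Second, the reported model does yield some variability, namely between-participant variance given Pre1 and the spread of the Pre2-to-Post change. That is correct, and the point is confined to the two components it cannot give.

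Third, a reader might infer that the pilot as a whole cannot supply these components. The documents do not support that. Protocol 1 mentions a second model, and the specification given first has session at three levels. Whether averaging applied to it is not said. Fitted to individual trials, it could give both. But it is not the model reported, and no variance output is specified for it.

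Fourth, a reader might infer that the Pre2/Post variance is merely inflated and should be dropped when planning a later study. That is wrong for the endpoint the plan names. Differences in response are part of the variance of a treated participant's change. In Setting B, ignoring misses, a participant's five-diameter mean change has variance 2(0.09) + 2(0.122)/5 = 0.229. Substituting the untreated session variance gives 2(0.01) + 2(0.122)/5 = 0.069. A single-arm pre-post study planned on the second figure would have about 0.069/0.229 = 30% of the size needed.

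Finally, SDs from completed insertions alone lose the slow tail beyond 30 seconds and can be too small. This stands, and counting the misses does not cure it.

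**Conclusion.** The point holds for the reported model. After averaging, it has no degrees of freedom for trial-to-trial variance. With Pre1 as a covariate, it has no pair of untreated sessions among its responses. This is an analysis gap: the design collected what is needed. The primary Pre2-to-Post estimate is not affected.

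The gain is uneven. The trial-to-trial SD could be known to within roughly 10% to 15% either way, depending on where the misses fell. The participant and session SDs rest on about 8 df and will stay imprecise.

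The exact factor of one third in the residual assumes that logs were averaged over three completed trials. The plan does not state the order of logging and averaging, and cells with misses rest on fewer trials, so the residual variance is also uneven across cells. The 8 df assumes that all 9 participants contribute to both baselines. That untreated session variance is among the variability meant is inferred from the adjoining sentence on stability. It is a modest but worthwhile addition that lets the pilot address a purpose it states.

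**What to change.** Keep the primary model unchanged and add a short paragraph to the analysis plan:

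- **Model.** Fit a supplementary mixed model to individual-trial log transit times from Pre1 and Pre2. Use fixed diameter and session, and random participant, participant-by-diameter, participant-by-session and participant-by-diameter-by-session effects. The participant-by-diameter term keeps stable differences in how a cylinder suits a given hand from looking like session variation. State in advance how the model will be simplified if it does not converge with 9 participants.
- **Report.** Give the between-participant, between-session and trial-to-trial SDs with 95% intervals, and a test-retest ICC with its interval for a stated unit, for example the session mean.
- **Misses.** Label the SDs as applying to completed insertions, give the number of misses beside them, and add a sensitivity analysis treating misses as right-censored at 30 seconds.
- **Use.** Report these components beside the variance of the Pre2-to-Post change. The change variance is relevant to planning a study on the pre-post endpoint. The untreated components inform measurement stability, the number of trials per session and any untreated comparison.

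The cost is one more model, its censored counterpart and a paragraph, all on data already coded. The downside is wide intervals for the participant and session SDs, which should be shown rather than hidden.
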